9.4.7.1 Drug-Drug Interactions

Listings of prohibited drugs are provided in [Listing 1](#), [Listing 2](#), and [Listing 3](#).

9.4.8 Treatment Compliance

Records of treatment compliance for each subject will be kept during the Treatment Period. CRAs will review treatment compliance during site visits and at the completion of the study.

9.4.9 Drug Supplies and Accountability

In compliance with local regulatory requirements, drug supplies will not be sent to the investigator (or if regionally required, the head of the medical institution or the designated pharmacist) until the following documentation has been received by the sponsor:

- A signed and dated confidentiality agreement
- A copy of the final protocol signature page, signed and dated by both the sponsor and investigator
- Written proof of approval of the protocol, the ICFs, and any other information provided to the subjects by the IRB/IEC for the institution where the study is to be conducted
- A copy of the IRB/IEC-approved ICF and any other documentation provided to the subjects to be used in this study
- The IRB/IEC membership list and statutes or Health and Human Services Assurance number
- A copy of the certification and a table of the normal laboratory ranges for the reference laboratory conducting the clinical laboratory tests required by this protocol
- An investigator-signed and dated Food and Drug Administration (FDA) Form FDA 1572, where applicable
- Financial Disclosure form(s) for the principal investigator and all subinvestigators listed on Form FDA 1572, where applicable

- Current medical license or proof of qualification of principal investigator (not required for sites outside North America if the qualification can be verified by their curriculum vitae) (revised per Amendment 02)
- A signed and dated Clinical Trial Agreement (CTA)
- A copy of the regulatory authority approval for the country in which the study is being conducted (if required), and the Import License (if required)

The investigator and the study staff (or if regionally required, the head of the medical institution or the designated pharmacist) will be responsible for the accountability of all study drugs (dispensing, inventory, and record keeping) following the sponsor's instructions and adherence to GCP guidelines as well as local or regional requirements.

Under no circumstances will the investigator allow the study drugs to be used other than as directed by this protocol. Study drugs will not be dispensed to any individual who is not enrolled in the study.

The site must maintain an accurate and timely record of the following: receipt of all study drugs, dispensing of study drugs to the subject, collection and reconciliation of unused study drugs that are either returned by the subjects or shipped to site but not dispensed to subjects, and return of reconciled study drugs to the sponsor or (where applicable) destruction of reconciled study drugs at the site. This includes, but may not be limited to: (a) documentation of receipt of study drugs, (b) study drugs dispensing/return reconciliation log, (c) study drugs accountability log, (d) all shipping service receipts, and (e) documentation of returns to the sponsor. All forms will be provided by the sponsor. Any comparable forms that the site wishes to use must be approved by the sponsor.

The study drugs and inventory records must be made available, upon request, for inspection by a designated representative of the sponsor or a representative of a health authority (eg, FDA, Medicines and Healthcare Regulatory Agency). As applicable, all unused study drugs and empty and partially empty containers from used study drugs are to be returned to the investigator (or if regionally required, the head of the medical institution or the designated pharmacist) by the subject and, together with unused study drugs that were shipped to the site but not dispensed to subjects, are to be returned to the sponsor's designated central or local depot(s) during the study or at the conclusion of the study, unless provision is made by the sponsor for destruction of study drugs and containers at the site. Destruction at the site will only occur under circumstances where regulation or supply type prohibits the return of study drugs to the central or local depot(s). Approval for destruction to occur at the site must be provided by the sponsor in advance. Upon completion of drug accountability and reconciliation procedures by the site's personnel and documentation procedures by the sponsor's personnel, study drugs that are to be returned to the sponsor's designated central or local depot(s) must be boxed, sealed, and shipped back to the central or local depot(s) following all local regulatory requirements. In some regions, study drugs may be removed from the site and hand delivered to the central or local depot by sponsor representatives. Where study drugs are approved for destruction at the site, destruction will occur following the site's standard procedures and certificates of destruction will be provided to the sponsor.

Drug accountability will be reviewed during site visits and at the completion of the study.

9.5 Study Assessments

9.5.1 Assessments

9.5.1.1 Demography

Subject demography information will be collected at the Screening Visit. Demography information includes date of birth (or age), sex, race/ethnicity, native language, handedness, and highest education level.

9.5.1.2 Baseline Assessments

9.5.1.2.1 MEDICAL HISTORY AND PHYSICAL EXAMINATIONS

Medical and surgical history, prior and concurrent medications including AChEI and memantine use, and current medical conditions will be recorded at the Screening Visit. All medical and surgical history within 10 years must be noted in the Medical History and Current Medical Conditions eCRF. Medical history will include history of cognitive impairment. Subjects will be asked about history of infections due to varicella zoster virus (chickenpox and herpes zoster/shingles) and HSV types 1 and 2 (orolabial herpes/cold sores and genital herpes, respectively). The medical history of such infections will include last outbreak, duration, relapse frequency, and severity. Subjects will also be asked about their vaccination history including vaccinations against varicella zoster virus and TB. The modified Hachinski ischemic score will be used to differentiate vascular dementia from dementia of Alzheimer's type.

Physical examinations will be performed as designated in [Table 4](#) and [Table 5](#). A complete physical examination will include evaluations of the head, eyes, ears, nose, throat, neck, chest (including heart and lungs), abdomen, limbs, a dermatologic exam, and a neurologic examination (including general status, cranial nerve function, motor system, coordination/cerebellar function, reflexes, and sensory system). (revised per Amendment 01) A urogenital examination will only be required in the presence of clinical symptoms related to this region. Documentation of the physical examination will be included in the source documentation at the site. Significant findings at the Screening Visit will be recorded on the Medical History and Current Medical Conditions eCRF. Changes from screening physical examination findings that meet the definition of an AE will be recorded on the AEs eCRF.

The CDR, MMSE, FAQ, and ADAS-cog14 are well-established clinical tools for use in the assessment of AD.

9.5.1.3 Efficacy Assessments

9.5.1.3.1 PSYCHOMETRIC ASSESSMENTS

CDR: The CDR is a clinical global rating scale requiring the interviewing of both the subject and a study partner who knows and has contact with the subject. The CDR is a

clinician-directed assessment of both cognition and function, and is intended to capture the state and therefore the disease stage of the individual. The CDR has been proposed as an acceptable approach for following disease progression and confirming treatment in AD.

The CDR assesses 6 domains of subject function: memory, orientation, judgment, and problem solving, community affairs, home and hobbies and personal care. Each of these items has a maximum possible score of 3 points and the total score is a sum of the item scores (sum of boxes) giving a total possible score of 0 to 18 with higher scores indicating more impairment.

For any given subject, every effort should be made to ensure that the CDR rater remains unchanged throughout the study. (revised per Amendment 04)

ISLT: The ISLT is a verbal learning and episodic memory test assessing both immediate and delayed recall. Subjects are read a list of 12 items that can be obtained at the local shopping center. Subjects are asked to recall as many of the items as possible and this immediate recall trial is repeated 3 times. After a delay of approximately 20 to 30 minutes, in which time the CBB will be performed as a distractor task, subjects are again asked to recall as many of the words on the shopping list as they can (ie, a delayed recall trial).

MMSE: A 30-point scale that measures orientation to time and place, registration, immediate and delayed recall, attention, language, and drawing. Scores range from 0 (most impaired) to 30 (no impairment).

ADAS-cog14: The ADAS-cog is the most widely used cognitive scale in AD clinical studies (Rosen, et al., 1984). The 14-item version will be used in the present study since it is considered more sensitive for less impaired populations such as MCI/Prodromal and mild AD subjects (Fleisher, et al., 2007). The Word Recall and Delayed Word Recall tasks from the ADAS-cog14 that will be used as secondary endpoints, employ methods that are similar to those used by the Consortium to Establish a Registry for Alzheimer's Disease (CERAD; Morris et al., 1989), (cited by Mohs et al., 1997). For Word Recall, 10 words, each printed in large letters on 1 card, are shown one at a time for 2 seconds each. The subject is instructed to read the words aloud. Immediately after reading the list, the subject is asked to recall the list aloud. This procedure is repeated 3 times and the immediate memory score is the average number of words incorrectly recalled during 3 trials. Word Recall is administered near the beginning of the ADAS-cog14. A few minutes later, the subject is asked to recall as many words as possible from the previously studied list. The total number of words incorrectly recalled on this Delayed Word Recall task ranges from 0 to 10. (revised per Amendment 03)

ADCOMS: ADCOMS is a composite score of 12 items from the CDR, MMSE, and ADAS-cog, and does not require any additional assessments. (revised per Amendment 06)

FAQ: The study partner provides performance ratings (from 0 to 3) on 10 complex activities of daily living performed within the preceding 4 weeks. Scores range from 0 (independent) to 30 (dependent).

Audio recordings will be made during the administration of a number of the scales above for possible central review (as permitted by local regulations).

9.5.1.3.2 VMRI AND fMRI

vMRI will be used to evaluate disease modification as indicated by measurements of brain atrophy, including the change from Baseline in terms of the measured hippocampal volume based upon the centralized measurement of the structure on repeated MRIs. A large number of studies, including the AD Neuroimaging Initiative, have shown that quantitative measurements of hippocampal, whole brain, and total ventricular volume provide robust and reliable biomarkers of disease progression, and potential for assessment of PD efficacy.

vMRI sequences will be collected for all subjects immediately following all safety MRI scans in the same imaging session. vMRI will be conducted at either 1.5T or 3T, and across multiple scanner types and the type of scanner used will be documented. vMRI analysis will be performed by a central imaging laboratory on MRI scans obtained at the times specified in [Table 4](#) and [Table 5](#), according to standard quality control and normalization procedures for measurements of the whole brain and total ventricular volume. Measurements of the right and left hippocampal volumes will be based on a validated algorithm and conducted in the same laboratory. Additional analysis of regions of interest and cortical thickness may also be performed.

Task-free fMRI can be used to assess the integrity of functional networks within the brain to help determine effects of disease on brain function. The additional sequence will be collected on all subjects who can keep their eyes open (to control for occipital input) and stay awake. Any subject who cannot fulfill this set of instructions for 7 to 10 minutes at the end of the vMRI scan will not be included in this exploratory study.

fMRI data will be used to generate connectivity maps based on critical anatomical regions, (eg, precuneus, inferior frontal sulcus) which can then be used within subject to determine the effect of elenbecostat on preserving connectivity known to degrade with progression of AD.

Descriptions and detailed instructions for all imaging can be found in the MRI imaging manual that will be provided to the study MRI imaging facilities.

9.5.1.3.3 CEREBROSPINAL FLUID SAMPLING

Amyloid CSF is 1 of the 2 methods available for screening to determine subject eligibility for the study. (revised per Amendment 03) Subjects who undergo the eligibility CSF sample collection or who consent to the CSF longitudinal substudy will be encouraged to stay at the site after completion of LP for medical observation. CSF sample(s) will be collected by LP (gravity drip method only) after fasting (preferred), or at least 2 hours after the most recent meal.

CSF samples at Visit 13 should be collected while the subject is still on the study drug and before the other visit assessments. All ED CSF samples need to be taken no later than 7 days

after the last dose of study drug. All CSF samples should be taken at approximately the same time of day as at the Screening Visit. (revised per Amendment 06)

Subjects who provide a CSF sample at Screening for amyloid eligibility purposes, but did not initially consent to the CSF longitudinal substudy may provide consent to the CSF longitudinal substudy at any point in time up to the CSF procedure at Visit 13 (or ED). INR results should be reviewed for subjects who consent to provide a CSF sample and are on concomitant anticoagulation/antiplatelet therapy, before LP; if they are assessed by the investigator to be at risk for bleeding, they are to be excluded from CSF collection. (revised per Amendments 01 and 02)

9.5.1.4 Pharmacokinetic, Pharmacodynamic, Pharmacogenomic, and Other Biomarker Assessments

9.5.1.4.1 PHARMACOKINETIC ASSESSMENTS

Blood samples will be collected for the determination of the concentrations of elenbecestat in all randomized subjects. Analyses of metabolite concentrations may be performed, depending on emerging data from other studies with elenbecestat. Samples from all subjects receiving active treatment will be analyzed. Placebo samples will be held in storage in the event that confirmatory analysis is requested. (revised per Amendment 04) Plasma concentrations of analytes will be quantified by liquid chromatography with tandem mass spectrometry methodology using a previously validated assay.

Blood samples will be collected as specified in [Table 4](#) and [Table 5](#). Two plasma PK samples will be obtained at each of the following visits: 1 sample at predose (trough) and another sample 1 to 6 hours postdose at Visits 3, 4, 6, 7, 9, and 11 and another sample 4 to 8 hours postdose at Visit 13 (or ED). Therefore, subjects or their study partners must be instructed not to take their study drug at home on the day the PK sampling is performed. Instead, subjects will take the study drug at the clinic after collection of the predose PK sample. At Visit 13 (or ED), the trough PK blood sample should be collected shortly before or after completing the LP for subjects participating in the CSF substudy. If the study drug is temporarily suspended, postdose PK samples will not be required. If at an ED Visit, the subject has already stopped study drug, postdose PK samples are not required. (revised per Amendment 06)

Blood will also be drawn where possible at the first report of an SAE or severe unexpected AE and at its resolution.

See the laboratory manual (to be supplied to study sites) for a description of the collection, handling, and shipping procedures for PK samples.

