- v: Site staff will contact the subject or the study partner the day before the PK blood sampling to provide instructions that subjects must not take their study drug at home on the day of the PK blood sampling. During this telephone contact with the subject or the study partner, the site staff should document the time that the subject took their study drug that day, ie, the day before the PK blood sampling.
- w: Two plasma PK samples will be obtained: 1 sample at predose (trough) and another sample 1 to 6 hours postdose at Visits 3, 4, 6, 7, 9, and 11 and another sample 4 to 8 hours postdose at Visit 13 (or ED). Therefore, subjects or their study partners must be instructed not to take their study drug at home on the day the PK sampling is performed. Instead, subjects will take the study drug at the clinic after collection of the predose PK sample. At Visit 13 (or ED), the PK blood sample should be collected shortly before or after completing the LP for subjects participating in the CSF substudy. If the study drug is temporarily suspended, postdose PK samples will not be required. If at an ED Visit, the subject has already stopped study drug, then postdose PK samples are not required.
- x: PD and exploratory biomarker blood samples should be collected at fasting or at least 2 hours after the most recent meal and, as far as is feasible, samples should be taken at the same time of day at all visits. Samples should be taken predose at Visits 2, 3, 4, 6, 7, 9, 11, 13 (or ED), 14, and 15. (revised per Amendments 01, 03, and 04)

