- y: For subjects who consent to participate in the CSF longitudinal substudy. Visit 13 (or ED) also includes blood PK and PD assessments and so the subject will be dosed at the clinic on these days. A CSF sample will be collected by LP between 4 and 8 hours postdose and at the same time of day as the subject's Screening LP (±1 hour). The CSF sample will be taken with the subject fasting (preferred) or at least 2 hours after the most recent meal. A gravity drip collection method must be used. If performed on the same day as the cognitive tests, the LP will be performed after the cognitive tests; the subject should rest and drink some fluid to hydrate after the cognitive tests and before the LP. Subjects will be encouraged to stay at the site after completion of LP for medical observation. The CSF sample will not be taken at the ED Visit if this visit occurs within 39 weeks of treatment or 3 months of a previous CSF sample. If at an ED Visit, the subject has already stopped study drug, then no dosing will take place, but the CSF sample will still be collected unless it was already collected within the past 3 months. Subjects receiving concomitant anticoagulation/antiplatelet therapy should have prothrombin time and INR (derived from prothrombin time) before LP; if they are assessed by the investigator to be at risk for bleeding, they are to be excluded from CSF collection. Note that subjects who are assessed by both amyloid PET and CSF are required to wait for a minimum of 48 hours between the 2 procedures. (revised per Amendments 01, 02, and 04)
- z: Subjects reporting AEs relating to abnormal dreams, nightmares, or sleep terror will be questioned on the nature, frequency, and impact of these events.
- aa: AEs that may signal drug abuse potential require a more detailed follow-up through completion of a specific eCRF form (Possible drug abuse potential form/questionnaire). Similarly, AEs

Table 5 Schedule of Procedures/Assessments in Study E2609-G000-301 (Revised per Amendments 05 and 06)

Phase Period	Randomization													Follow-Up			UNS Visit ^d
	Treatment												ED ^b	14 ^c	15 ^c		
Visit ^a	2	3	4	5	6	7	8	9	10	11	12	13					
Day	1	15	29	57	85	183	274	365	456	547	638	729		757	813		
Week	1	3	5	9	13	27	40	53	66	79	92	105		109	117		
Weeks elapsed since 1st dose	0	2	4	8	12	26	39	52	65	78	91	104		108	116		
Nominal months elapsed since 1st dose	0		1	2	3	6	9	12	15	18	21	24		25	27		
Procedures/ Assessments																	

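### At Visit 13, Section 9.5.1.4.1 ties the predose (trough) PK sample to a lumbar puncture that Table 5 places 4 to 8 hours after the dose; both rules cannot be followed

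*Protocol*

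**What the plan says.** Section 9.5.1.4.1 (Pharmacokinetic Assessments) schedules two plasma samples at Visit 13 or the early discontinuation (ED) visit. One is predose, which the section calls the trough. The second is described as "another sample 4 to 8 hours postdose at Visit 13 (or ED"). The dose is taken between the two: "subjects will take the study drug at the clinic after collection of the predose PK sample". For the CSF substudy the section then adds that "the trough PK blood sample should be collected shortly before or after completing the LP for subjects participating in the CSF substudy".

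Table 5 (Section 9.5.2.1) covers the same visit in two footnotes. Footnote y states that "Visit 13 (or ED) also includes blood PK and PD assessments and so the subject will be dosed at the clinic on these days", and that "A CSF sample will be collected by LP between 4 and 8 hours postdose". Footnote w repeats the pairing sentence of Section 9.5.1.4.1 without the word trough: "At Visit 13 (or ED), the PK blood sample should be collected shortly before or after completing the LP".

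Other current sections fix the order of the LP within the visit, not its hours from dose. Sections 9.1.2, 9.1.2.1 and 9.5.1.3.3 place CSF collection ahead of the other visit assessments. Footnote y places the LP after the cognitive tests when both fall on the same day.

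**The concern.** A predose sample cannot sit next to a procedure that takes place hours after the dose. A site reading Section 9.5.1.4.1, and the sections that put CSF first, has grounds to do the LP before the in-clinic dose. A site reading Table 5 has grounds to do it 4 to 8 hours later. A third site may keep the LP late, draw blood beside it, and enter that blood as the trough.

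Section 9.2.4 limits the CSF substudy to a single timepoint at 24 months, so a mistimed LP has no second chance. Section 9.7.1.7.2 relates CSF biomarker levels to plasma PK parameters and to CSF drug concentrations, and Section 9.7.1.7.1 plans summaries of plasma and CSF concentrations. Mixed LP timing across sites would add spread to those relationships that has nothing to do with biology. Mislabelled samples would blur the trough summaries.

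**Working it through.** The protocol gives no figure for this point, so there is none to reproduce. The check is timing arithmetic on the current text only; older text reproduced in the same file is not used.

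**Inputs**
- Trough = predose sample; dose taken in clinic after it (Section 9.5.1.4.1; Table 5 footnote w).
- Second plasma sample: 4 to 8 h postdose at Visit 13 (same two places).
- LP: 4 to 8 h postdose (footnote y).
- Dosing once daily in the morning (Section 9.4.1), so a predose time is taken as about 24 h after the previous dose.

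**Consistency of the rules.** Set the in-clinic dose at t = 0. The trough is at T ≤ 0 and the LP at L between 4 and 8.
- Smallest gap: L − T ≥ 4 − 0 = 4 h.
- At the end of the window: L − T ≥ 8 − 0 = 8 h.
- T is always less than L, so the trough can never come after the LP, although Section 9.5.1.4.1 allows either order.

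The three rules (trough predose, LP at 4 to 8 h, trough next to the LP) have no common solution. Each way out breaks one of them:
1. *Keep the trough predose and next to the LP.* The LP moves to about 24 h after the previous dose and leaves footnote y's window. The shift is 24 − 8 = 16 h to 24 − 4 = 20 h.
2. *Keep the LP at 4 to 8 h and draw the named sample beside it.* That sample is 4 to 8 h postdose and is not a trough.
3. *Keep the trough predose and the LP at 4 to 8 h.* The pairing in Section 9.5.1.4.1 is abandoned. The second plasma sample lies in the same window as the LP, 0 to 8 − 4 = 4 h from it, but Section 9.5.1.4.1 does not tie it to the LP.

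**Wording side by side.** Footnote w's version, "the PK blood sample should be collected shortly before or after completing the LP", can be read as the postdose sample and then agrees with footnote y. Section 9.5.1.4.1 names the trough and cannot. The section and the schedule table therefore disagree on which sample is paired.

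**Where the conflict does not arise.** For an ED subject who has already stopped drug, no dose is given and no postdose sample is required, so a single sample beside the LP is workable.

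**The case against.** The best reply is that sites will find a sensible path: predose trough, dose, then LP and second blood draw in the same 4-to-8-hour window. Section 9.5.1.4.1 itself refers to Table 5 for sampling times. That stands as a likely reading, but it requires the site to disregard an explicit instruction.

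Several stronger inferences are tempting and are not supported:
- *Plasma and CSF are no longer concurrent.* In ways 1 and 2 above the blood is drawn beside the LP; in way 3 a plasma sample is within 4 h of it. What can be lost is uniform LP timing or correct labelling, not the plasma level itself.
- *The 4-to-8-hour plasma window exists to match the LP.* No section says so. It applies at Visit 13 generally, not only to substudy subjects.
- *Footnote y governs, so one word needs changing.* The documents do not settle this. Section 9.5.1.4.1 and the sections putting CSF first carry Amendment 06 tags, while footnote y's own tag stops at Amendment 04, so a deliberate move of the LP to the start of the visit is possible. Against that, Table 5's heading cites Amendment 06, and Appendix 5 Table 9 footnote k keeps an LP at 4 to 8 h postdose for the Extension Phase.
- *Every substudy subject's PK data are damaged.* Randomization is about 1:1 and placebo PK samples are stored, not analysed, so the drug-concentration effect is confined to the active arm.
- *Mislabelled samples wreck the PK analysis.* The plan is a population model using dosing history, and the previous day's dose time is recorded (footnote v). The exposed parts are the concentration summaries and the graphical PK/PD work. Nor can such samples be called near-peak, since the protocol gives no time of peak concentration.

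**Conclusion.** The contradiction is real, lies within the current text, and holds for CSF-substudy subjects still on drug at Visit 13 or ED. The trough precedes an in-window LP by at least 4 hours, so Section 9.5.1.4.1 cannot be followed together with footnote y. If sites split, the single on-treatment Core Study CSF sample differs by 16 to 20 hours in time from last dose, assuming a 24-hour dosing interval. How many sites would split is unknown, and the protocol does not say how far CSF drug or Aβ levels move over that interval, so the effect can be sized in hours only.

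The consequence is avoidable variation in the CSF PK/PD analyses and possible mislabelling in the trough summaries, all in an optional substudy. The primary endpoint, the key secondary endpoints and the sample size are not affected, nor are ED subjects already off drug.

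**What to change.** Reconcile Sections 9.1.2, 9.1.2.1, 9.5.1.3.3 and 9.5.1.4.1 with Table 5 footnotes w and y so that they give one LP time relative to dose, one order relative to the other assessments, and one named plasma sample paired with the LP. Which LP time is intended is for the sponsor to confirm:
- If the 4-to-8-hour postdose LP is kept, Section 9.5.1.4.1 should name the 4-to-8-hour postdose sample as the partner and leave the trough before the dose, and the three sections that put CSF collection ahead of the other assessments should be brought into line.
- If an LP before the dose is intended, footnote y should say so, and footnote w should name the trough.

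In either case, state that for an ED subject already off drug the single PK sample is drawn beside the LP. Use actual times from last dose for both plasma and CSF in the PK/PD analysis, and flag Visit 13 samples already collected under the conflicting wording.

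The cost is a few wording changes in the next amendment, a laboratory-manual note, and a check of recorded times for samples already taken. No new visits or samples are needed.
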